8. SAFETY ANALYSES

The safety analyses will be based on the Intent-to-Treat (ITT) population (as defined in Section 4: Analysis Populations), unless otherwise specified.

8.1. Adverse Events Analyses

Adverse events analyses including the analysis of adverse events (AEs), Serious (SAEs) and other significant AEs will be based on GSK Core Data Standards. The details of the planned displays are provided in [Appendix 9: List of Data Displays](#).

Adverse events (AEs) will be collected starting with the first administration of single-blind study treatment. Adverse events during the pre-treatment period include those with date of onset prior to study treatment initiation (first dose date). Adverse events during the on-treatment period include those with date of onset on or after the date of double-blind study treatment initiation and on or before the double-blind study treatment termination date. Adverse events during the post-treatment period include those with date of onset after the double-blind study treatment termination date.

The AE text recorded in the eCRF will be coded using the Medical Dictionary for Regulatory Activities (MedDRA) coding dictionary. The version of MedDRA used in reporting will be noted in a footnote of the AE overview table.

For the standard AE tables, the number and percentage of participants with all AEs (regardless of causality) will be summarized for each treatment group by System Organ Class (SOC) and Preferred Term (PT). Results will be displayed in the order of decreasing frequency, both across SOC and within SOC. A SOC will not be included if no AEs in that SOC are reported. If the total incidence for any two or more adverse events is equal, the events will be presented in alphabetical order.

Adverse events will also be listed.

8.2. Adverse Events of Special Interest Analyses

A comprehensive list of MedDRA terms based on clinical review will be used to identify AEs of special interest to FF. Changes to the MedDRA dictionary may occur between the start of the study and the time of reporting and/or emerging data from on-going studies may highlight additional adverse events of special interest, therefore the list of terms to be used for each event of interest and the specific events of interest will be based on the safety review team (SRT) agreements in place at the time of reporting. The details of the planned displays are provided in [Appendix 9: List of Data Displays](#).

The number and percentage of participants with AEs of special interest will be summarized for each treatment group by special interest term, subgroup and PT. The ordering of the special interest terms, the subgroups and the PTs within them will all be in descending order of total incidence. If the total incidence for any two or more AEs is equal, the events will be presented in alphabetical order.

8.3. Asthma Exacerbations

An exacerbation is defined as deterioration of asthma requiring the use of systemic corticosteroids (tablets, suspension, or injection) for at least 3 days or a single depot corticosteroid injection, or an in-patient hospitalisation or emergency department (ED) visit due to asthma that required systemic corticosteroids.

Asthma exacerbations will not be recorded as an AE unless they meet the definition of an SAE.

The incidence of exacerbations will be summarized by treatment group and listed.

8.4. Oropharyngeal Examination

Oropharyngeal examinations will be conducted according to the Protocol Defined Schedule of Events (see Section 11.2.1). Any adverse finding will be recorded as an AE or SAE and included in summaries and listings of AEs/SAEs.

8.5. Other Safety Measures

All investigational product (IP) inhaler malfunction data for participants reporting at least one IP inhaler malfunction will be listed. Pneumonia data (on- and post-treatment) will be summarised. All pneumonia data collected on the pneumonia eCRF page will be listed. For any deaths, cardiovascular events or liver events reported during the study, Integrated Data Standards Library (IDSL) standards for reporting will be followed for all data collected in the eCRF.

A summary of risks plot will be produced summarizing the following AE information:

- SAE (any)
- Withdrawal due to AE (including events leading to permanent discontinuation of study drug and/or withdrawal from the study)
- AESI (any)

Individual AESI will also be summarized:

- Pneumonia
- Hypersensitivity
- Local steroid effects
- Ocular effects
- Effects on glucose
- Adrenal suppression

The frequencies, relative risk and corresponding 95% CI for FF 50 vs. Placebo will be displayed for the ITT population (as defined in Section 4: Analysis Populations). Calculations of the relative risks and 95% CIs are described in Section 11.6.4.

9. EFFICACY ANALYSES

The efficacy analyses will be based on the Intent-to-Treat (ITT) population (as defined in Section 4: Analysis Populations), unless otherwise specified.

The following parameters will be used as a measure of compliance to help identify non-adherence and/or poorly controlled asthma:

- Daily asthma symptom scores
- Daily PEF (measured in the morning only)
- Daily albuterol/salbutamol use. Number of inhalations of rescue albuterol/salbutamol inhalation aerosol used during the day and night. Note: Rescue medication taken as preventative treatment before exercise will be excluded from this count and should not be entered into the daily eDiary
- C-ACT score at Visit 1 (Screening), Visit 5 (Randomisation), and Visit 18

Each morning, a parent or caregiver will assess the daytime symptoms from the previous day and the night-time symptoms from the night just ended. Each 24-hour period will incorporate the morning symptom assessment with the evening symptom assessment recorded on that date but, will refer to the day immediately before. Therefore, the symptom scores recorded on the date of randomisation (i.e., Day 1) will in fact reflect the 24 hours prior to randomisation (Day -1), and the first day of symptoms on treatment will be associated with the date following the day of randomisation (Day 2).

The baseline morning PEF will be defined in a similar manner. Since PEF assessments are recorded before morning study treatment is administered, the same rules as described above will also apply to PEF. In other words, the first day of on-treatment PEF will be associated with the date following the day of randomisation (Day 2).

9.1. Change from Baseline in the Percentage of Rescue/Symptom Free 24-Hour Periods Over the Double-Blind Treatment Period

The change from baseline in the percentage of rescue-free and symptom-free days over the double-blind treatment period will be summarised by treatment. The baseline percentage of rescue-free and symptom free 24-hour periods will be as defined in Section 5.2: Baseline Definitions. Change from baseline will be defined as the difference between the average over the double-blind treatment period and the baseline value.

The efficacy endpoints relating to daily diary assessments will be calculated from all available data over the period of interest. No imputation will be considered with respect to missing daily diary data. See also Section 11.6.5.

No formal statistical analysis is planned

9.2. Change from Baseline in Morning Peak Expiratory Flow Over the Double-Blind Treatment Period

The change from baseline in the morning Peak Expiratory Flow (PEF) over the double-blind treatment period will be summarised by treatment group. Baseline is as defined in Section 5.2: Baseline Definitions. Change from baseline will be defined as the difference between the average over the double-blind treatment period and the baseline value.

The efficacy endpoints relating to daily diary assessments will be calculated from all available data over the period of interest. No imputation will be considered with respect to missing daily diary data.

No formal statistical analysis is planned.

9.3. C-ACT Score

C-ACT scores will be summarized by treatment at each planned visit (Visit 1, Visit 5 and Visit 18), and will include summaries of the number of participants at each visit whose asthma is considered controlled (i.e., who have a C-ACT score at that visit of 20 or more). In addition, the change from baseline (Visit 5) C-ACT score at endpoint (Visit 18) will be summarized by treatment. Change from baseline will be defined as the difference between the value of the measure at Visit 18 and the baseline value. If Visit 5 or Visit 18 data is not available, change from baseline will not be calculated.

No formal statistical analysis is planned.

11. APPENDICES

11.1. Appendix 1: Exclusions from Per Protocol Population

Instream and final analysis population reviews as per SOP 130050 are not planned for this study because it does not include a Per-Protocol population.

11.2. Appendix 2: Schedule of Activities

11.2.1. Protocol Defined Schedule of Events

Visit Number (*Child Visits)	Screening/Baseline					Double-blind Treatment													Follow Up		T/D	W/D	
	1*	2	3*	4	5*	6*	7*	8*	9*	10	11	12*	13	14	15*	16	17	18*	19	20*	*	*	
Week Number	-16	-12	-8	-4	0	4	8	12	16	20	24	28	32	36	40	44	48	52	+4	+ 8			
Day (All visits to occur within -5 to +2 days of specified day)	-112	-84	-56	-28	1	29	57	85	113	141	169	197	225	253	281	309	337	365	+28	+56			
Written Informed Consent ¹ for Study and PGx Sample	X																						
Assign Subject Number	X																						
Subject Demography	X																						
Medical (Including Asthma) History	X																						
Therapy History	X																						
Physical Examination	X																						
Tanner Staging	X				X							X						X		X	X	X	X
Stadiometry ²	X		X		X	X	X	X	X			X			X			X		X	X	X	X
Body Weight Measurement	X		X		X			X				X			X			X		X	X	X	X
BMI Measurement	X		X		X			X				X			X			X		X	X	X	X
Inclusion/Exclusion Criteria Verified	X																						

CONFIDENTIAL

HZA114971

	Screening/Baseline					Double-blind Treatment													Follow Up		T/D	W/D	
Visit Number (*Child Visits)	1*	2	3*	4	5*	6*	7*	8*	9*	10	11	12*	13	14	15*	16	17	18*	19	20*	*	*	
Week Number	-16	-12	-8	-4	0	4	8	12	16	20	24	28	32	36	40	44	48	52	+4	+8			
Day (All visits to occur within -5 to +2 days of specified day)	-112	-84	-56	-28	1	29	57	85	113	141	169	197	225	253	281	309	337	365	+28	+56			
Completion of daily e-diary (PEF, asthma symptoms and compliance with study medication) ³	X ⁴	X	X	X	X	X	X	X	X	X	X	X	X	X	X	X	X	X	X	X	X	X	X
Assess e-diary and compliance	X	X	X	X	X	X	X	X	X	X	X	X	X	X	X	X	X	X	X	X	X	X	X
Spirometry-generated FEV ₁	X																						
cACT	X				X													X			X	X	
Concomitant Medication	X	X	X	X	X	X	X	X	X	X	X	X	X	X	X	X	X	X	X	X	X	X	X
Pharmacogenetic Sample ⁵						X (One Sample Only)																	
Adverse Event Assessment		X	X	X	X	X	X	X	X	X	X	X	X	X	X	X	X	X	X	X	X	X	X
Serious Adverse Event Assessment	X	X	X	X	X	X	X	X	X	X	X	X	X	X	X	X	X	X	X	X	X	X	X
Oropharyngeal Exam	X		X		X	X	X	X	X			X			X			X		X	X	X	X
Hand/Wrist X-Ray Scheduled		↔																					
Bone Age Result					X																		
Assess Randomisation Criteria					X																		

CONFIDENTIAL

HZA114971

	Screening/Baseline					Double-blind Treatment													Follow Up		T/D	W/D
Visit Number (*Child Visits)	1*	2	3*	4	5*	6*	7*	8*	9*	10	11	12*	13	14	15*	16	17	18*	19	20*	*	*
Week Number	-16	-12	-8	-4	0	4	8	12	16	20	24	28	32	36	40	44	48	52	+4	+ 8		
Day (All visits to occur within -5 to +2 days of specified day)	-112	-84	-56	-28	1	29	57	85	113	141	169	197	225	253	281	309	337	365	+28	+56		
Assign Randomisation Number					X																	
Dispense Open-label Montelukast	X	X	X	X	X	X	X	X	X	X	X	X	X	X	X	X	X	X	X	X		
Dispense Single-Blind Treatment	X	X	X	X																		
Dispense Double- Blind Treatment					X	X	X	X	X	X	X	X	X	X	X	X	X					
Dispense Rescue Med (PRN)	X	X	X	X	X	X	X	X	X	X	X	X	X	X	X	X	X	X	X	X		
Collect All Medications		X	X	X	X	X	X	X	X	X	X	X	X	X	X	X	X	X	X	X	X	X

1. If applicable, subject must be able and willing to give assent to take part in the study according to the local requirement. The study investigator is accountable for determining a child's capacity to assent to participation in a research study, taking into consideration any standards set by the responsible IEC/IRB.
2. Subjects must attend the clinic for scheduled visits when stadiometry will be assessed. Subjects' parents/guardians will need to attend the clinic every month to collect/return diaries and study medication.
3. Subjects will be required to record compliance with study medication (single-blind run-in treatment, double-blind treatment and open-label montelukast) each day in the e-diary. Daily salbutamol use, asthma symptom scores and PEF will be recorded in the e-diary each day and will be collected at each visit. Note: After the Early Treatment Discontinuation Visit subjects will no longer be required to complete the e-diary.
4. AT Visit 1, e-diary will be dispensed only.
5. Saliva (2mL) is spit into the DNA self-collection kit. This should ideally be taken as soon after randomisation (Visit 5) as possible but may be taken at any other visit after randomisation, if necessary. Genetics consent must be obtained prior to PGx sampling.

* = Child Visit – these visits are where the child (subject) must attend the clinic.

NOTE: W/D = Early Withdrawal Visit and T/D = Early Treatment Discontinuation Visit

11.3. Appendix 3: Assessment Windows

11.3.1. Definitions of Assessment Windows for Analyses

Clinic visits are scheduled to take place as specified in [Appendix 2: Schedule of Activities](#). Note that all visits should occur within -5 to +2 days of the specified visit day. Individual measurements will be reported based on the visits they are assigned to in the study database without adjustment.

11.4. Appendix 4: Study Phases and Treatment Emergent Adverse Events

11.4.1. Study Phases

11.4.1.1. Study Phases for Assessments

Assessments will be classified according to time of occurrence relative to the start and/or stop date of the double-blind study treatment. The earliest and latest exposure double-blind treatment start and stop dates will be used to determine whether an assessment was pre-treatment, on-treatment or post-treatment. If it is not possible to tell whether an assessment or event was on-treatment or not it will be considered as on-treatment.

Study Phase	Definition
Pre-Treatment	Assessment Date \leq Start Date of Double-Blind Treatment - 1
On-Treatment	Start Date of Double-Blind Treatment \leq Assessment Date \leq Stop Date of Double-Blind Treatment + 1
Post-Treatment	Assessment Date \geq Stop Date of Double-Blind Treatment + 2

Note: For the analyses of growth velocity defined in Section 7: Growth Analyses, “off-treatment” refers to height data collected during the double-blind treatment period (i.e., after Visit 5 up to and including Visit 18/EW/TD) while participants were not receiving randomised double-blind treatment.

11.4.1.2. Study Phases for Concomitant Medication

A medication will be summarized in every study period (pre-, on-, or post-treatment) in which it was taken, so a medication that was started during the run-in period and stopped during the double-blind treatment period will appear in both the pre-treatment and the on-treatment summaries.

Pre-treatment will be considered prior to and until the day of double-blind treatment start. On-treatment will be considered to be from the day after the double-blind treatment start date until the double-blind treatment stop date.

11.4.1.3. Study Phases for Asthma Exacerbations

Asthma exacerbations will be classified according to the time of occurrence relative to start and/or stop date of the double-blind study treatment.

Study Phase	Definition
Pre-Treatment	Exacerbation Onset Date \leq Start Date of Double-Blind Treatment - 1
On-Treatment	Start Date of Double-Blind Treatment \leq Exacerbation Onset Date \leq Stop Date of Double-Blind Treatment + 1
Post-Treatment	Exacerbation Onset Date \geq Stop Date of Double-Blind Treatment + 2

11.4.1.4. Study Phases for eDiary

Diary measurements will be classified according to the time of occurrence relative to start and/or stop date of the double-blind study treatment. Note that rescue medication use, daytime symptoms, and overnight symptoms are recorded daily for the previous day.

Study Phase	Definition
Pre-Treatment	Date of Measurement \leq Start Date of Double-Blind Treatment
On-Treatment	Start Date of Double-Blind Treatment $<$ Date of Measurement \leq Stop Date of Double-Blind Treatment + 1
Post-Treatment	Date of Measurement \geq Stop Date of Double-Blind Treatment + 2

11.4.2. Treatment Emergent Flag for Adverse Events

Adverse Events will be classified according to the time of occurrence relative to start and/or stop date of the double-blind study treatment.

Treatment state	Definition
Pre-Treatment	AE Start Date \leq Start Date of Double-Blind Treatment - 1
On-Treatment	Start Date of Double-Blind Treatment \leq AE Start Date \leq Stop Date of Double-Blind Treatment + 1
Post-Treatment	AE Start Date \geq Stop Date of Double-Blind Treatment + 2
Onset Time Since 1 st Dose (Days)	Time Since 1st Dose will be derived as follows: If Start Date of Double-Blind Treatment $>$ AE Onset Date, then \Rightarrow AE Onset Date – Start Date of Double-Blind Treatment If Start Date of Double-Blind Treatment \leq AE Onset Date, then \Rightarrow AE Onset Date – Start Date of Double-Blind Treatment + 1 If Double-Blind Treatment Start Date or AE Onset Date are missing, then \Rightarrow missing
Duration (Days)	AE resolution date – AE onset date + 1
Drug-Related	If relationship is marked 'YES' OR value is missing.

NOTE: If the study treatment stop date is missing then the AE will be considered to be on-treatment.

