6.3. Treatment Assignment

All subjects will receive a single-blind placebo inhaler during the 16-week run-in period.

Subjects will be stratified by country and be assigned to double-blind treatment (either inhaled FF 50 mcg or inhaled placebo) in accordance with the randomisation schedule generated prior to the start of the study, using validated software.

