where *Total Number of Inhalations Taken* is the total number of doses taken from all inhalers, *Expected Inhalations* is equal to 1 and *Start Date* and *Stop Date* are the earliest treatment start date and the latest treatment stop date recorded for all of the inhalers used in the calculation.

Participants who are either under- (<80%) or over- (>120%) compliant over the run-in and double-blind treatment periods according to both the diary card and the inhaler dose counter, will be identified. The numbers of these participants, as well as the number of participants whose compliance is unknown, will be summarized by treatment.

Extent of Exposure
 
 • Duration of exposure (days) to double-blind study treatment will be calculated as: 
 ○ Double-Blind Treatment Stop Date – Double-Blind Treatment Start Date + 1 • Participants who were randomised but did not report a double-blind treatment start/stop date, will have missing exposure. • Duration of post-treatment time (days) spent in the study will be calculated as: 
 ○ Study Conclusion Date – Double-Blind Treatment Stop Date • Duration of total time (days) spent in the study since first dose will be calculated as: 
 ○ Study Conclusion Date – Double-Blind Treatment Start Date + 1 • Double-blind treatment start and stop dates used will be the earliest (start) and latest (stop) of all dates recorded for the participant. Study conclusion is defined as completion or withdrawal, as applicable.

Concomitant Medications
 
 • Concomitant medications will be coded using the GSK Drug coding dictionary. Summaries of the number and percentage of participants taking concomitant medications will be displayed by ingredient without regard to Anatomical Therapeutic Chemical (ATC) classifications. These summaries will include single-ingredient medications and will present multi-ingredient medications according to the combination of the component ingredients. Summaries will be split into asthma and non-asthma concomitant medications, as well as into those taken pre-, on-, and post-treatment (as described in Section 11.4.1).

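### The missing-stop-date note in SAP 11.4.2 has no onset-date condition, so read literally it turns run-in adverse events into on-treatment events

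*SAP*

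**What the plan says.** The table in SAP 11.4.2 has three phase rows. Pre-Treatment is "AE Start Date \leq Start Date of Double-Blind Treatment - 1", that is, onset at least one day before double-blind treatment began. On-Treatment runs from the double-blind start date to one day after the stop date. Post-Treatment is anything later. The note beneath the table reads: "NOTE: If the study treatment stop date is missing then the AE will be considered to be on-treatment".

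Three other places bear on it:

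- **SAP 8.1** says that "Adverse events (AEs) will be collected starting with the first administration of single-blind study treatment", so run-in events will be in the data. It then classes an event with onset before the first dose date as pre-treatment.
- **SAP 11.4.1.1** gives the general default: "If it is not possible to tell whether an assessment or event was on-treatment or not it will be considered as on-treatment".
- **SAP 11.4.1.3** applies the same start and stop limits to asthma exacerbations but has no note on a missing stop date.

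The run-in is a placebo period for every child. Protocol 6.3 states: "All subjects will receive a single-blind placebo inhaler during the 16-week run-in period".

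**The concern.** A missing stop date leaves one thing unknown: whether an event after the double-blind start fell before or after treatment ended. It adds no doubt about an event that began before the start date. The note nevertheless assigns both kinds of event to the on-treatment phase, because a missing stop date is its only condition.

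A programmer who follows the note exactly would move a child's placebo run-in events into the on-treatment displays of the arm to which the child was later randomised. The displays split by this flag include the on-treatment adverse event and serious adverse event tables (2.39 and 2.48), the common-event tables (2.44 and 2.45) and the special-interest tables (2.52 and 2.53). The last two cover only on- and post-treatment events, so a run-in event could enter them only through the note.

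**Working it through.** The plan states no figure to reproduce. The check applies the rules to every possible onset day.

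**Inputs.** Run-in of 16 weeks = 112 days; double-blind period to Day 365; follow-up of 8 weeks = 56 days (Time and Events Table). Total onset days: 112 + 365 + 56 = 533.

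**Rules compared.** (a) The table rows alone. (b) The rows plus the note as written. (c) The rows plus the note limited to events starting on or after the double-blind start date.

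| Stop date | Rule | Pre | On | Post | Undetermined |
|---|---|---|---|---|---|
| Day 365 | a, b and c | 112 | 366 | 55 | 0 |
| Missing | a: rows alone | 112 | 0 | 0 | 421 |
| Missing | b: note as written | 0 | 533 | 0 | 0 |
| Missing | c: note limited | 112 | 421 | 0 | 0 |

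With a known stop date, the on-treatment window is 365 + 1 = 366 days and the three rules agree. With no stop date, the rows alone still settle all 112 run-in days and leave 365 + 56 = 421 days open. The note as written overrides the Pre-Treatment row on all 112 run-in days. Those days equal 112 / 366 = 31% of a full on-treatment window. Rule (c) settles the 421 open days in the same way as the note and leaves the run-in days where the rows put them.

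**A sign of the conflict within the section.** The onset-time formula in SAP 11.4.2 gives a negative value when onset precedes the double-blind start. Rule (b) would therefore produce on-treatment events with a negative time since first dose.

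**Size per affected child.** The documents do not say how many children lack a stop date, so the effect is given per child. About 225 children are to be randomised per arm, so one child moves an any-event percentage by at most 1 / 225 = 0.44 points. For an expected value, assume 1 to 3 adverse events per child-year (an assumption; the documents give no rate) at a constant rate:

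- P(at least one run-in event) = 1 − exp(−rate × 16/52)
- Rate 1: 1 − exp(−0.308) = 0.265. Rate 3: 1 − exp(−0.923) = 0.603.
- Expected shift per affected child: 0.265 × 0.44 = 0.12 points to 0.603 × 0.44 = 0.27 points.

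These are upper figures for the any-event count, because a child who also has a true on-treatment event is already counted there.

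**The case against.** The strongest reply is that the note is a tie-breaker. The Pre-Treatment row settles a run-in event before the stop date comes into play, SAP 8.1 says the same, and SAP 11.4.1.1 limits the default to cases that cannot be told apart. Read together, these make the note a choice between on- and post-treatment only. That is probably the intent. It stands as an account of intent but not of the wording: the note carries no such limit, and a rule that misclassifies events when followed exactly should be corrected.

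The reply on scope stands in full. SAP 11.6.1 takes the latest stop date from the compliance log and the treatment discontinuation page, inhalers are dispensed and collected throughout the double-blind period, and data cleaning precedes analysis (SAP 3.2). A wholly missing stop date should be rare.

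A reader might infer more than the documents support:

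- **That the SAP expects such children.** SAP 11.6.2 says: "Participants who were randomised but did not report a double-blind treatment start/stop date, will have missing exposure". This is a contingency. It may concern children who were randomised but never dosed, who are outside the ITT population and so outside these tables.
- **That follow-up events are also misclassified.** When the stop date is unknown, their phase may be genuinely uncertain, and counting them as on-treatment matches the default in SAP 11.4.1.1.
- **That the shift could push events over the 3% common-event threshold.** That threshold applies to individual event terms. A count of children with any run-in event is spread over many terms and cannot be compared with it.
- **That the arms would be biased against each other.** Run-in events precede randomisation and are balanced in expectation. Bias would need stop dates to be missing unequally between arms, and nothing in the documents shows that.

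**Conclusion.** The point holds as a wording error in a stated rule. With the stop date missing, the note contradicts the Pre-Treatment row of its own table and the definition in SAP 8.1, and it goes beyond the default in SAP 11.4.1.1.

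The practical effect is probably very small. It needs an ITT child with a known double-blind start date, no stop date in either source, at least one run-in event, and a programmer who follows the note literally. The ceiling of 0.44 points per affected child rests on the planned 225 per arm; the expected 0.12 to 0.27 points rests also on the assumed event rate. If the start date is missing too, the general default in SAP 11.4.1.1 may properly apply. The flag concerns adverse events only, so the primary and supportive growth analyses are untouched.

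**What to change.** Replace the note in SAP 11.4.2 with:

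> If the double-blind treatment stop date is missing, an AE with start date on or after the double-blind treatment start date will be considered on-treatment; an AE with start date before the double-blind treatment start date remains pre-treatment.

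This also replaces the note's reference to study treatment with the table's term, double-blind treatment. The alignment is useful because Protocol 6.1 lets study treatment mean any combination of the products, including montelukast, which continues through follow-up.

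The cost is one sentence in the SAP and one condition in the derivation program, best made before unblinding. Nothing changes for any child whose stop date is known.
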